3.2. Pooling Algorithm for Analysis Centers

NA

3.3. Analysis Sets

All analyses, except for subject disposition, will use data for the safety analysis set. Demographics will also be summarized based on all randomized set and subject disposition will be based on all subjects.

3.3.1. Efficacy Analysis Set(s)

There will be no efficacy analysis set.

3.3.1.1. Primary Efficacy Analysis Set

NA

3.3.1.2. Secondary Efficacy Analysis Set

NA

3.3.2. All Randomized Set

This will include all randomized subjects.

3.3.3. Safety Analysis Set

This will include all randomized subjects who received at least 1 dose of study medication. This population will be used for all analyses, including any DMC analyses. All subjects will be analyzed according to treatment they received by first study drug dispensation.

3.3.4. Pharmacokinetics Analysis Set

The PK analysis set will consist of all subjects in the safety analysis set with available plasma concentrations.

3.3.5. Pharmacodynamics Analysis Set

NA

3.4. Definition of Subgroups

Data will be summarized in addition by age group of 2 to 5 years of age, 6 to 9 years of age, 10 to 12 years of age, and 13 to 15 years of age, separately. For height, Z-scores for height, height velocity and height velocity Z-scores, data will also be summarized by 2 to 9 years of age.

4. INTERIM ANALYSIS AND DATA MONITORING COMMITTEE REVIEW

There will be no interim analyses, but an external, independent DMC will be established to review safety data on a quarterly basis or less frequent basis (but not more than six months) when deemed necessary and ensure the continuing safety of the subjects enrolled in this study. Additional adhoc meetings can be requested by the DMC or the Sponsor. After the review, the DMC will make recommendations regarding the continuation of the study. The details will be provided in a separate DMC charter.

The DMC is comprised of four clinicians and one statistician. The Chairperson and one member are pediatric endocrinologists with expertise in bone, growth and maturation; the other two clinicians are a pediatric nephrologist and a pediatric neurologist. Mention one member is statistician. The DMC responsibilities, authorities, and procedures will be documented in its charter.

The safety analyses will be performed by Statistical Support Group (SSG) independent of the Sponsor. The output tables in the data package will be displayed by each age group (2-5, 6-9, 10- 12, and 13-15) and overall. All data and output should be held in strict confidentiality with access to DMC and SSG only before they can be transferred to the Sponsor.

Separate outputs will be generated for the open- and closed-sessions of the DMC meetings. The outputs in the data package for the open-session will be unblinded, except for Ultra Sound, DEXA and height analyses. These will present summaries for all subjects combined (e.g., tables will only present a Total column). All outputs in the data package for the closed-session will be unblinded and will present the data by the subjects' true treatment group assignment.

Before each scheduled DMC meeting, data cut-off dates (6 to 8 weeks prior to the meeting) will be identified and the clinical database will be made as clean as possible, with particular focus on safety data. For the purpose of the DMC review of the results, all available data needed for the TLFs up to the time of data cut-off dates, unless otherwise specified will be included in the TLFs.

The Contract Research Organization, PAREXEL, will provide the SDTM datasets containing the electronic case report form (eCRF) data, the cognitive battery data (computerized cognitive battery as well as NEPSY testing), and the central laboratory data to the SSG statistician using the Janssen MBOX. The DEXA and US data will be provided directly to the SSG statistician by Bioclinica. Given that this is an open-label study, the treatment assignment will be included in the CRF data.

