7.7. Seizure Count 25

7.8. Cognitive, Developmental, and Behavioral Assessments 25

7.9.	Adverse Events.....	27
7.10.	Clinical Laboratory Tests.....	28
7.11.	Vital Signs and Physical Examination Findings.....	28
7.12.	Electrocardiogram.....	29
7.13.	Other Safety Parameters.....	29
8.	PHARMACOKINETICS/PHARMACODYNAMICS.....	30
8.1.	Pharmacokinetics.....	30
8.2.	Immune Response.....	30
8.3.	Pharmacodynamics.....	30
8.4.	Pharmacokinetic/Pharmacodynamic Relationships.....	30
9.	HEALTH ECONOMICS.....	30
10.	APPENDICES.....	30
	Appendix 1: Cogstate Pediatric Normative Data.....	31
	Appendix 2: Markedly Abnormal Laboratory Parameter Values.....	34
11.	URINALYSIS.....	43
	Appendix 3: AE of clinical interest.....	44
	Appendix 4: Vineland scores.....	73
12.	VARIABLE DESCRIPTION.....	75
	Appendix 5: CBCL scoring instruction.....	81
	Appendix 6: Method for computing height velocity values and z-scores for individual subjects.....	89
	Appendix 7: List of generic and brand names of AED medications.....	99

LIST OF IN-TEXT TABLES

Table 1:	Time and Events Schedule	11
Table 2:	Definition of windows for height, weight, exposure, vital signs, laboratory tests, physical examination and neurological examinations:.....	15
Table 3:	Definition of windows for Renal Ultrasound, Cogstate, Tanner Staging and 24 hour urine collection:	15
Table 4:	Definition of windows for C-SSRS:.....	16
Table 5:	Definition of windows for Vineland Scale and CBCL:.....	16
Table 6:	Definition of windows for Bone age:.....	16
Table 7:	Definition of windows for seizure count:	16
Table 8:	Definition of windows for DEXA:.....	17
Table 9:	Definition of windows for Pharmacokinetics.....	17
Table 10:	Clinically Important Vital Sign Values.....	29

AMENDMENT HISTORY

SAP version	issue date
Original	December 03, 2019
1 st Amendment	February 24, 2020
2 nd Amendment	May 13, 2020
3 rd Amendment	June 4, 2020

The overall reason for the amendment 1:

Major: 1. re-insertion of MMRM analysis in a pre-specified way of analysis & 2. additional sensitivity analysis for subjects who took concomitant AED after the first study medication intake.

MMRM analysis:

An MMRM analysis is included as sensitivity analysis to explore longitudinal safety data and will be analyzed in the following order.

1. The model includes treatment group, study center, age group (4 age groups), visit, treatment-by- visit interaction, baseline measure, and baseline-by-visit interaction with the unstructured covariance matrix.

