1. CHANGES IN CONDUCT OF THE STUDY

On 12 December 2018, the independent Data Monitoring Committee (DMC) recommended to stop the TOPMATEPY4067 study because of futility of study enrollment. On 12 August 2019, Janssen has received the US FDA decision as follows:

- Stop enrolling new subjects at all sites and discontinue the study at all the sites that do not have either subject under study treatment or subjects who require a repeat bone mineral density (BMD) measurement 6 months after discontinuing study treatment.
- All sites with any subject on treatment in the study should continue following the subject according to the protocol until treatment has been completed, the subject has discontinued prematurely, or a repeat DEXA scan (which is indicated 6 months after treatment discontinuation) has been completed.

The US FDA decision is based on the slow rate of study enrollment of subjects despite continuous efforts to improve recruitment in the study. The decision is not related to any safety issues.

Interim analyses on the key endpoints (change in BMD z-score at Month 12, change in height z-score at Month 12 and change in weight z-score at Month 12) were conducted on 13 December 2018. This SAP has been modified based on the early termination of the study.

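### SAP section 4 denies the December 2018 interim that section 1 reports, and every SAP version that changes the protocol's rules for the three key endpoints is later than that interim

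*SAP*

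**What the plan says.** SAP section 4 opens with "There will be no interim analyses, but an external, independent DMC will be established to review safety data" and then describes DMC reviews at intervals of up to six months. SAP section 1 says otherwise: "Interim analyses on the key endpoints (change in BMD z-score at Month 12, change in height z-score at Month 12", together with the same measure for weight, "were conducted on 13 December 2018". It adds that on the previous day the DMC "recommended to stop the TOPMATEPY4067 study because of futility of study enrollment". It attributes the regulator's decision, received on 12 August 2019, to slow recruitment: "The decision is not related to any safety issues". The section ends with "This SAP has been modified based on the early termination of the study".

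The SAP amendment history dates the original SAP "December 03, 2019" and lists three amendments in 2020. The first is summarised in part as "re-insertion of MMRM analysis in a pre-specified way of analysis". Protocol section 11.5 provides for DMC safety review at least twice a year and plans no interim analysis of the key endpoints. SAP section 2.3 keeps a hypothesis of equal effect that the study is to test, while section 7 plans no formal testing and reports 95% CIs for treatment differences.

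**The concern.** Both statements about the interim stand in current SAP text and cannot both be true. No section gives the data cut, the number of children per arm, whether results were produced by arm, or which roles saw them. The study is open-label, and SAP section 4 notes that treatment assignment is in the CRF data.

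This matters because the analysis rules for the same three endpoints were written down, in the versions listed, after that analysis. A reader cannot tell whether the model, the baseline window and the handling of added AEDs were chosen with knowledge of the interim results. Two of the changes also alter what the lead estimate means. A DEXA baseline taken after dosing has begun is no longer a pre-treatment value, and including data after an added AED mixes monotherapy with combination therapy although the objective concerns monotherapy.

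**Working it through.** **1. Order of events.**
- 3 November 2017: protocol Amendment INT-6, the last analysis rules in these documents dated before the interim.
- 12 December 2018: DMC recommendation to stop.
- 13 December 2018: interim on the three key endpoints, one day later.
- 12 August 2019: regulator's decision received, about eight months later.
- 3 December 2019: original SAP, 365 − 10 = 355 days after the interim.
- 24 February, 13 May and 4 June 2020: SAP amendments 1 to 3.

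So 4 of 4 listed SAP versions follow the interim.

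**2. Rules for the key endpoints, side by side.**

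| Rule | Protocol (before the interim) | Current SAP (after the interim) |
|---|---|---|
| Model | Section 11.4: MMRM is the analysis for longitudinal endpoints, with treatment, age group, visit, treatment-by-visit, baseline, baseline-by-visit and unstructured covariance | Section 7: MMRM is a sensitivity analysis; study center added; section 3.2 gives no center pooling rule |
| DEXA baseline | Time and Events Schedule, footnote c: Day 1 procedures other than dispensing are done before randomization | Section 3.1, Table 8: Day -35 to Day 30 |
| Added AED | Sections 3.1, 3.2.2 and 8: data before the added AED form the primary analysis, later data a secondary one | Section 7: dropping data after the added AED is a sensitivity analysis |

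The protocol schedule also prints a ±7-day window against the baseline visit. Even if that window were read as allowing a late scan, it would end at Day 1 + 7 = Day 8, not Day 30.

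**3. What a Day 30 DEXA baseline does.** Protocol section 6 has the first dose taken on the evening of Day 1, so a scan on Days 2 to 30 is on treatment. With Month 12 targeted at Day 360, the change is measured over 360 − 30 = 330 days instead of 360 − 1 = 359 days. That is 29/359 = 8.1% shorter, and any early drug effect is absorbed into the baseline. The amendment 2 summary says the widening brings in 4 children. Against the planned 2 × 100 = 200 completers that is 4/200 = 2%. Enrolment stopped early, so the real share may be larger. The documents give neither the final number nor the arms of these 4 children.

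**4. Whether the study was planned as a test.** SAP section 2.4 sets the size by CI precision: 100/(1 − 0.29) = 140.8, so 141 per arm and 282 in total. The half-width is 1.96 × SD × √(2/n):
- height: 1.96 × 0.28 × √(2/53) = 0.107 (stated 0.11)
- weight: 1.96 × 0.43 × √(2/100) = 0.119 (stated 0.12)
- BMD: 1.96 × 0.40 × √(2/100) = 0.111 (stated 0.12, a separate small discrepancy)

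No alpha and no interim success rule appear. The planning basis is estimation, in line with section 7 and at odds with section 2.3.

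**The case against.** The case on the other side is substantial.

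- **Disclosure.** Section 1 gives the interim's date and endpoints and says the SAP was changed after early termination. A reader might infer that the final analysis is passed off as a single look under rules fixed in advance. The documents do not support that: nothing calls it single, and the word pre-specified occurs only in the amendment summary, about the MMRM and its ordered fallbacks.
- **Error rate.** A reader might infer an inflated false-positive rate from two unadjusted looks. That needs CIs used as tests and an interim able to support a claim. Section 7 plans no formal testing, and no interim rule exists. The DMC recommendation preceded the interim and cited enrolment. If stopping did not depend on results, the final CIs keep nominal coverage. This objection stands.
- **Result-driven choices.** A reader might infer that the changes followed the interim results. The documents do not show this. The MMRM is mostly the protocol's own model, with center the only new term in the main model. The DEXA window has a stated data-capture reason. The pre-AED restriction is older than the interim; only its demotion is later. Section 4 has an independent support group run the analyses and holds output to that group and the DMC until transfer to the sponsor.
- **Earlier text.** The wording about modification and re-insertion suggests an earlier SAP outside the listed history.

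The access rule is not tied to the 13 December analysis and gives no transfer date, and no earlier SAP is identified. Missing documentation therefore remains, along with three departures from the protocol that have not been placed in relation to the interim.

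**Conclusion.** The concern holds in a limited form. The first sentence of SAP section 4 is wrong on the SAP's own account, and three rules for the key endpoints differ from the protocol in SAP versions that all follow the interim. This should be corrected, but it does not invalidate the final intervals. For a given analysis rule, and taking the enrolment-based reason for stopping at face value, the 95% CIs keep nominal coverage, so no type I error figure belongs in this point.

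The known size is three endpoints, three rules and 4 children with a late DEXA scan. The effect on the estimates cannot be calculated, because the documents give neither the interim data cut nor the number of children with an added AED. The conclusion assumes that the listed SAP history is complete. If an earlier SAP dated before 13 December 2018 contains any of these rules, those rules would not need a post-interim label.

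**What to change.** 1. Replace the first sentence of SAP section 4 with the facts of the 13 December 2018 interim: data cut, number analysed per arm, whether results were by arm, and which roles saw them and when. Identify any SAP text that existed before that date.
2. For Month 12 change in BMD, height and weight Z-score, lead with the protocol 11.4 MMRM and its terms, the Day 1 pre-treatment baseline, and the protocol's restriction to data before an AED is added. That restriction should refer to AEDs added after study drug starts, not to a baseline AED being tapered under protocol section 8.
3. Report the study-center model, the DEXA baseline to Day 30 and the analysis including data after an added AED as sensitivity analyses, labelled as specified after the interim.
4. State that the CIs are unadjusted and serve estimation, and reconcile section 2.3 with section 7 on whether a hypothesis is tested.

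The cost is SAP wording and one extra table setting lead and sensitivity estimates side by side. The downside is that the 4 late-scanned children enter BMD change only in a sensitivity analysis.

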5. SUBJECT INFORMATION

5.1. Demographics and Baseline Characteristics

Subject demographics and baseline disease characteristics will be listed and summarized for the randomized analysis set by treatment group. Descriptive statistics (mean, standard deviation, median, minimum, and maximum) will be presented for age, height, weight, body mass index (BMI), and years since diagnosis of epilepsy. Frequency counts and percentages will be presented for categorical variables sex, age group (2-5 years, 6-9 years, 10-12 years, 13-15 years), ethnicity, race, geographic region, seizure types present within the last 2 years, seizure occurred within the last 2 years beyond 3 or 5 month, seizure occurred in last 3 or 5 months and any AED drug/therapy at study entry and bicarbonate categories. Bicarbonate values are categorized as low (<20 mEq/L at screening) and non-low bicarbonate values (\geq 20 mEq/L at screening).

Age in years will be used from eCRF. In case of missing eCRF for age, 15th of the month will be used as day. Missing day and month at date of birth will be imputed by June 30. Years since diagnosis of epilepsy will be calculated based on year of Day 1 minus year of diagnosis (if both in the same year it will be 0).

- Age calculation:
 - For Height and Weight Z-Scores, it is given in CDC guidance document, age is in month with one decimal.
 - For demographics, it is floor (ICF date minus birth date)/365.25), age is in full years.
 - For Vineland it is floor ((intck ('month', birth date, visit date)-(day (visit date)<day(birth date))))), age is in full month.
 - For CBCL it is floor (visit date minus birth date)/365.25), age is in full years.
 - For Cogstate it is floor (visit date minus birth date)/365.25), age is in full years.
 - For vital signs it is floor (visit date minus birth date)/365.25), age is in full years.
 - For labs it is floor (visit date minus birth date)/365.25), age is in full years.
 - Age for determination of max daily dose for Topiramate or Levetiracetam it is floor (date of dosing minus birth date)/365.25), age is in full years.
- BMI is calculated as weight (kg) / height (m)².

Geographic region will be summarized as North America, South America, Europe and Asia Pacific.

- North America: US, Canada
- South America: Argentina, Mexico
- Europe: Belgium, France, Germany, Hungary, Italy, Poland, Russian Federation, Austria, South Africa, UK
- Asia Pacific: Australia, Taiwan, Philippines

